At the second study call, participants ($N=608$) will be randomized to one level of each of 4 factors (see Table 2): 1) Medication Type (Varenicline vs. C-NRT), 2) Preparation Medication (4 weeks vs. Standard), 3) Medication Duration (Extended vs. Standard), and 4) Counseling (Intensive vs. Minimal). Participants will complete phone assessments one week pre-quit, during the first week post-target quit date (TQD) and at Weeks 2, 4, 12, 20, 26, and 52 post-TQD.

Assessments

Call 1. At Call 1, participants will complete the phone screen, complete the oral consent and HIPAA authorization process, and complete a brief demographics assessment. After this call, participants will be mailed a Study Information Sheet that contains all of the information related to the study. They will also be sent information on how to use WebEx so they can have video visits if they so choose.

Call 2. Participants will answer questions about their smoking and other tobacco use history, their self-efficacy and motivation, their physical and emotional health, the impact of Covid-19 on their life and their beliefs about Covid-19 and smoking, and their satisfaction with their health care and they will complete the Fagerström Test of Cigarette Dependence¹¹⁷ (see Table 1). Participants will be randomized to their treatment condition, set a target quit date, and be educated about their assigned medication (including how and when to request refills).

Calls 3-6. Participants will receive a call one week pre-quit, during the first week post-target quit date (TQD) and at Weeks 2 and 4 from their Health Counselor. This research staff member will assess: a daily smoking calendar using timeline follow-back¹¹⁸, medication use (as appropriate

PROTOCOL
 "P01 Cessation Screening Study"
 PI: [name].; UW-CTRI Grant:

based on study condition), use of alternative nicotine products (e.g., e-cigarettes), withdrawal, self-efficacy, and adverse events. We will recommend dosage/use alterations as per good clinical practice if participants experience adverse events. Participants will be referred to their primary care physician should they require medical consultation. Participants will also receive smoking cessation counseling as appropriate, based on their assigned treatment condition. If the call does not include treatment it will not be conducted by the participant's health counselor (i.e., Calls 5 and 6 for those in the Minimal Counseling condition).

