Calls 7-10. All participants will get calls at Weeks 12, 20, 26 and 52 from research personnel who did not provide treatment to determine: smoking status (7-day point prevalence and daily calendar using timeline follow-back); use of alternative nicotine products (e.g., e-cigarettes); study medication use in the last 7 days; and withdrawal, self-efficacy, and adverse events (if using study medication). Calls 7, 9, and 10 will also assess the impact of Covid-19 on their life and their beliefs about Covid-19 and smoking. These assessment calls will not include counseling. If participants do not complete the 26 or 52-week assessment calls, we will send a brief assessment to them in the mail with a return envelope for them, and/or via text/email if the participant has consented to text/email communications, to report their smoking status. If participants report a serious adverse event or if they discontinue their study medication due to an adverse event, that information will be emailed to their primary care provider in the EHR by the Care Manager to enhance clinical care.

Table 1. Schedule of Cessation Screening Project Assessments and Interventions

| Assessments | | | Wk -1 | Day 2 | Wk 2 | Wk 4 | Wk 12 | Wk 20 | Wk 26 | Wk 52 |
|--------------------------------------|-----|----|-------|-------|------|------|-------|-------|----------------|----------------|
| | C1* | C2 | C3 | C4 | C5 | C6 | C7 | C8 | C9 | C10 |
| Eligibility screening | X | | | | | | | | | |
| Verbal consent and info sheet mailed | X | | | | | | | | | |
| Demographics | X | | | | | | | | | |
| Smoking history | | X | | | | | | | | |
| Covid-19 questions | | X | | | | | X | | X | X |
| Self-efficacy/ motivation | | X | X | X | X | X | X | X | X | X |
| Random assignment to treatment | X | | | | | | | | | |
| Tobacco dependence | | X | | | | | | | | |
| Health, alcohol use | | X | | | | | | | | |
| Withdrawal | X | X | X | X | X | X | X | X | X | X |
| Smoking status | X | X | X | X | X | X | X | X | X | X |
| Use of other tobacco products | X | X | X | X | X | X | X | X | X | X |
| Cannabis use | X | | | | X | X | | | X | |
| Medication use [†] | | | X | X | X | X | X | X | X | |
| Adverse events [†] | | | X | X | X | X | X | X | X | |
| Patient satisfaction | X | | | | | | X | | X | |
| Medication education and mailing | X | | | | | | | | | |
| Set target quit day ^{**} | | X | | | | | | | | |
| Intensive counseling (phone/video) | | | X | X | X | X | | | | |

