varenicline up to 35 days prior to the quit day is safe and effective. Participants assigned to the "OFF" level start their C-NRT use on their TQD or the standard Preparation varenicline, which starts 1-week pre-TQD (see Table 2).

Medication Duration: Extended vs. Standard. After Call 2, all participants will be mailed enough medication to get through the first month post-TQD and instructed to call a toll-free study number to have their refills mailed to them. Half of participants will be assigned to the Extended Duration (i.e., the "ON" condition); these participants will be able to use varenicline for 23 weeks post-TQD (24 weeks post-TQD if also randomized to preparation meds) or use C-NRT for 24 weeks post-TQD (see Table 2). The other half of participants will have varenicline for 11 weeks post-TQD (12 weeks post-TQD if also randomized to preparation meds) or C-NRT for 12 weeks post-TQD. We will urge all participants to use all of their study medication, regardless of whether they are abstinent or not.

Counseling: Intensive vs. Minimal. Half of the participants will be assigned to the Intensive Counseling condition and will receive four 15-20-minute counseling sessions occurring 1 week prequit, during the first week post-TQD and during Weeks 2 and 4 (see Table 1). During the first counseling call, the HC and participant will create a quit plan that the HC will then mail to the participant following the call. The counseling will be provided either via HIPAA-secure WebEx

Table 2. Medication Dosing

| | | Cessation Medication: Standard Duration (12 Weeks) | Cessation Medication: Extended Duration (24 Weeks) |
|-------------------------|------------------------|--|---|
| Varenicline | | 
No Preparation Meds:
 
 ▪ Days 1-3: 0.5 mg pill QD ▪ Days 4-7: 0.5 mg pill BID ▪ Day 8 (TQD)-Week 11: 1 mg pill BID 
Preparation Meds:
 
 ▪ Days 1-3: 0.5 mg pill QD ▪ Days 4-7: 0.5 mg pill BID ▪ Day 8-Week 16: 1 mg pill BID (TQD in Week 4) | 
No Preparation Meds:
 
 ▪ Days 1-3: 0.5 mg pill QD ▪ Days 4-7: 0.5 mg pill BID ▪ Day 8 (TQD)-Week 23: 1 mg pill BID 
Preparation Meds
 
 ▪ Days 1-3: 0.5 mg pill QD ▪ Days 4-7: 0.5 mg pill BID ▪ Day 8-Week 28: 1 mg pill BID (TQD in Week 4) |

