Primary Aim 2: To identify two optimized smoking cessation treatments: one for varenicline and one for C-NRT. Data on both the 12-month abstinence effect sizes and costs of the different intervention components and combinations of components will be examined and multiple criteria decision analysis will be used to determine how to use each medication so that it is highly effective and but low in cost.

Secondary Aims: To determine: 1) whether person factors (e.g., sex, dependence, psychiatric history) moderate response to different treatment strategies; and 2) which proximal effects of each treatment factor mediate its long-term benefits; and 3) the main and interactive effects of the cessation interventions on cost-effectiveness and the cost-effectiveness of the optimal combinations of components for each medication type.

Implementation Challenges: Pandemic and Varenicline

Study recruitment began in November 2020.

In June 2021 Pfizer found that some lots of varenicline contained elevated levels of a novel nitrosamine that exceeded the level thought to be safe by the FDA for traditional nitrosamines. Therefore, we briefly paused recruitment. When we resumed recruitment, all participants were randomized to the C-NRT level of the Medication Type factor until November 2021 when we received IRB approval to use FDA-approved generic varenicline. When we were able to procure FDA approved varenicline, we changed our randomization ratio on this factor to 2:1 varenicline to C-NRT. When FDA initiated the varenicline recall, there were 42 participants actively taking

varenicline; 26 participants opted to switch to C-NRT and 16 stopped all medication. These 42 participants will not be included in the main outcome analyses.

We experienced significant implementation challenges with collecting in-person breath samples for biochemical verification of abstinence. In September 2023 we transitioned from using exhaled CO to verify abstinence ($\text{CO} < 6\text{ppm}$) to using cotinine assays on mailed saliva samples to verify abstinence ($\text{cotinine} \leq 10\text{ng/mL}$).

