The robustness of the optimized treatments will then be evaluated with regard to other factors such as patient preference and implementation/burden data (e.g., required clinician/staff time). We will conduct sensitivity analyses that vary both the criteria and weightings (derived from stakeholder data) to examine the robustness of the identified optimized care packages.

Secondary Aims Analyses. Analysis of moderators of abstinence outcomes will use regression tree analyses that can identify differential treatment responses in 6- and 12-month abstinence. Candidate moderators of treatment effects on abstinence will include: living with a smoker, biological sex, age, use of other tobacco products at baseline, cigarettes per day at baseline, and education, and psychiatric history. Candidate mediators of cessation treatment effects will be: medication use and side effects, attendance at counseling sessions, withdrawal symptoms (e.g., craving, negative affect, anhedonia), and cessation self-efficacy. Treatment effects will be modeled as main effects and 2-way interactions with the outcomes being 6- and 12-month biochemically confirmed 7-day point-prevalence abstinence. Mediation analyses will use bootstrapped confidence intervals of the mediated effect. Care will be taken to preserve mediator/outcome temporal priority and the occurrence of smoking during the quit attempt will be statistically controlled. Mediation models will include multiple mediators and will use methods developed for use with dynamic mediator assessments (maximum likelihood estimation using hierarchical linear modeling: HLM 5.04).

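### At Weeks 2 and 4 the self-reported mediators go to the treating counselor in Intensive but to someone else in Minimal, and the SAP's Counseling mediation analysis does not allow for this

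*Protocol*

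**What the plan says.** **Who calls.** In the Protocol's Assessments section (Calls 3-6), the calls include those "at Weeks 2 and 4 from their Health Counselor". The caller collects a daily smoking calendar, medication use, other nicotine use, and "withdrawal, self-efficacy, and adverse events. We will recommend dosage/use alterations" on the same call. There is one exception: "If the call does not include treatment it will not be conducted by the participant's health counselor". The Protocol then names the calls and the level concerned: "health counselor (i.e., Calls 5 and 6 for those in the Minimal Counseling condition").

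**Who has a session.** The Counseling paragraph under Interventions says that Intensive participants "will receive four 15-20-minute counseling sessions occurring 1 week prequit, during the first week post-TQD and during Weeks 2 and 4". Table 1 shows Minimal counseling at Calls 3 and 4 only.

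**Later calls.** "All participants will get calls at Weeks 12, 20, 26 and 52 from research personnel who did not provide treatment" (Protocol, Calls 7-10).

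**What the SAP does with the data.** Its Secondary Aims include finding "which proximal effects of each treatment factor mediate its long-term benefits". Under Secondary Aims Analyses the candidate mediators are medication use and side effects, session attendance, "withdrawal symptoms (e.g., craving, negative affect, anhedonia), and cessation self-efficacy". They are to be modelled as repeated assessments, with 6- and 12-month confirmed abstinence as outcomes. The safeguards named are correct time order of mediator and outcome, and statistical control for smoking during the quit attempt. The caller is not mentioned.

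**The concern.** These mediators are what participants tell a caller. Someone may describe confidence, craving, pill-taking or lapses differently to the counselor who is treating them than to another member of staff. At Weeks 2 and 4 that difference coincides with the Counseling level, so any reporting shift enters the treatment-to-mediator path and can create or mask an apparent mediated effect.

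The planned control for smoking during the quit attempt does not remove the problem. For the days covered at Calls 5 and 6, the calendar is taken by the same unequal callers.

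What is at stake is the interpretation of one secondary aim for one factor. A result that Intensive counseling works by raising self-efficacy could not be told apart from participants sounding more confident to their own counselor.

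**Working it through.** **1. The plan's own figure.** The only power statement concerns abstinence, not mediation, and this point does not depend on it. It reproduces with n = 304 per level, two-sided α = .05 and z = [Δ√n − 1.96√(2p̄q̄)] / √(p₁q₁ + p₂q₂).
- 15% vs 25%: (1.744 − 1.109)/0.561 = 1.13, power 0.871 (stated .87).
- 20% vs 30%: (1.744 − 1.200)/0.608 = 0.89, power 0.814 (stated .81).

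**2. Caller by call and level** (Protocol, Calls 3-6, Calls 7-10, Counseling paragraph, Table 1).

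| Call | Time | Intensive | Minimal | Match |
|---|---|---|---|---|
| 3 | 1 week pre-quit | own counselor, session | own counselor, session | yes |
| 4 | first week post-TQD | own counselor, session | own counselor, session | yes |
| 5 | Week 2 | own counselor, session | not own counselor | **no** |
| 6 | Week 4 | own counselor, session | not own counselor | **no** |
| 7-10 | Weeks 12, 20, 26, 52 | non-treating staff | non-treating staff | yes |

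**3. Consequence.** Let a be the true effect of Counseling on a mediator and δ the shift in reporting from being asked by one's own counselor. At Calls 5 and 6 the difference between levels estimates a + δ. With b the mediator-to-outcome path, the estimated indirect effect is (a + δ)·b. Caller and level coincide completely at these calls, so no covariate can split a from δ there. Only the choice of calls can.

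**4. Other factors.** Medication Type, Preparation and Duration are crossed with Counseling. Each of their levels contains both kinds of caller, so their main effects are not aliased with caller. An interaction with Counseling is exposed if δ differs across levels of the other factor.

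**5. Illustration of size.** The documents give no value for δ, so everything here is assumed, including that δ applies in full to the rating used. Take a = 0 and n per level = (538 − 42)/2 = 248, assuming an equal split. Then SE = √(2/248) = 0.0898 SD, and the probability of a significant path is 1 − Φ(1.96 − δ/SE) + Φ(−1.96 − δ/SE).

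| δ (SD) | 0 | 0.05 | 0.1 | 0.2 | 0.3 |
|---|---|---|---|---|---|
| n = 248 | 0.05 | 0.086 | 0.200 | 0.605 | 0.916 |
| n = 304 (planned) | 0.05 | 0.095 | 0.234 | 0.694 | 0.959 |

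A simulation of the indirect effect used 248 per level, 600 replicates, a Monte Carlo interval, an assumed log-odds of 0.5 per SD from mediator to abstinence, and an intercept of −1.4 (about 20% abstinent). The interval excluded zero in 5%, 19%, 61% and 90% of trials for δ = 0, 0.1, 0.2 and 0.3.

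**6. Dilution if ratings are pooled.** Averaging Calls 3-7 gives 2/5 of δ: 0.04 to 0.12 SD for δ of 0.1 to 0.3. Adding Week 20 (Calls 3-8) gives 2/6: 0.03 to 0.10 SD. The SAP does not say which calls supply the mediators, and it plans a hierarchical model, not an average. Neither fraction is therefore the plan's own.

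**The case against.** The case on the other side is substantial, and much of it stands.

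- **Bias is not shown.** A reader might infer that the Counseling mediation result will be wrong. The documents establish a difference in caller and nothing about whether reports shift, which way, or by how much. Zero is possible. This stands: the claim is that the two explanations cannot be separated, not that one is true.
- **The difference may be only familiarity.** The Protocol bars only the participant's own counselor, and the footnote to Table 1 allows calls by Health Counselors or other research staff. Another counselor might make the Minimal calls. This stands, but it leaves the aliasing in place. Nor do counselors rate anything: the measures are self-reports.
- **Missing data.** A reader might also infer that ratings go missing differently by level, because an Intensive session and its rating share a call. A missed Call 5 or 6 loses the rating in Minimal too, and both levels are paid for each assessment. The documents do not show a difference.
- **Dropping Weeks 2 and 4 would hurt.** They are the only ratings taken while the number of sessions differs. At Calls 3 and 4 both levels have had equal numbers of sessions, and Week 12 is eight weeks after the last Intensive one. This stands and is the reason not to demote those ratings.
- **Limited importance.** Mediation is listed among the secondary aims in the SAP but not in the Protocol. The SAP reports interim differences of 0.0 to 4.9 points for three unnamed factors; if Counseling is one of them, there may be little to mediate. This limits the priority, but the SAP still commits to the analysis.

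**Conclusion.** The point holds as one of interpretation. At two calls the caller coincides completely with Counseling level, the SAP uses measures collected there as candidate mediators, and neither of its named safeguards addresses the caller. If the analysis relies on Weeks 2 and 4, a Counseling-to-mediator path cannot be distinguished from differential reporting.

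The size is unknown. The probabilities of 0.20 to 0.92 rest on an assumed shift of 0.1 to 0.3 SD, no true effect, an equal split and full use of the affected rating. They show that a modest shift would matter, not that one exists.

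The reach is narrow. It covers Counseling and its interactions, and only mediators obtained by asking the participant; session attendance is not among these. A reader might extend the point to the primary result. The documents do not support that: 12-month abstinence is biochemically confirmed, its call is made by non-treating staff at both levels, and the main effects of the other three factors are not aliased with caller.

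**What to change.** In the SAP, Secondary Aims Analyses, add for mediation of Counseling and its interactions:

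1. Prespecify an analysis restricted to mediator ratings taken after counseling begins and with matched callers: Call 4, Week 12 and, where temporal order allows, Week 20.
2. Report it beside the analysis using all calls, without ranking one above the other.
3. Claim mediation through a self-reported mediator only if the two agree in direction and rough size. Otherwise state that the caller difference may explain the result.
4. State which calls supply the mediators and the early-smoking control, and note that the calendars at Calls 5 and 6 come from unequal callers.

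The all-calls analysis can stay as planned for the main effects of the other three factors.

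The cost is SAP wording and one extra analysis of data already in the collection schedule. The matched-caller version will be less sensitive, because it has no ratings during Weeks 2-4, when the number of sessions differs. Disagreement between the two analyses would therefore leave the question open; it would not prove a reporting effect.

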| Minimal counseling (phone/video) | | | X | X | | | | | | |
| Cotinine/anabasine | | | | | | | | | X ^a | X ^a |

*C1 will be conducted by the healthcare system Care Manager. All other calls will be conducted by research Health Counselors or other research staff

**The TQD will be set either 5 weeks from C2 to allow a week for medication to be delivered and 4 weeks for prequit medication use for those in the prequit medication condition, or 2 weeks from the C2 to allow a week for medication to be delivered and 1 week for prequit medication if the participant is in the

varenicline no-pre-quit medication condition

[†]Medication use and adverse events will be assessed for participants currently receiving study medication (this will vary by treatment condition)

[‡]All participants who report 7-day point-prevalence abstinence will be asked to provide a saliva sample to biochemically confirm abstinence.

Month 6 and 12 Biochemical Confirmation. Participants who report 7-day point-prevalence abstinence at the Month 6 and 12 follow-up call will be mailed a saliva collection kit with instructions on how to collect a saliva sample and mail it back to the Center. These saliva samples will be sent to a lab to assess the level of cotinine (a metabolite of nicotine and biomarker for smoking and other sources of nicotine). Please note, if participants have a detectable level of anabasine (a biomarker specific for combustible tobacco), we will also collect those results. Participants who report abstinence in the last 7 days at this visit but have a cotinine level >10ng/mL or who do not have provide a cotinine result will be considered to be smoking. When a participant demonstrates biochemically confirmed abstinence, that information will be conveyed to the primary care provider by the Care Manager via either email in the electronic health record or by changing the electronic health record smoking status.

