To facilitate safety, participants who may not be medically appropriate to use either pharmacotherapy will not be included in the study (e.g., no severe renal disease, no allergic reactions to tested pharmacotherapies). Once enrolled, follow-up protocols will assess for medication side effects and unanticipated health events at all study contacts. We will recommend dosage/use alterations as per good clinical practice if the participant experiences symptoms of nicotine toxicity or other troublesome side effects once they begin medication treatment. We will refer participants their primary care provider as needed. Should either excessive risk to study participants and/or lack of measurable benefit to study participants be determined, the study will be stopped and all participants notified in a manner appropriate to the nature of the risk and/or lack of benefit.

Participants who are pregnant or planning to become pregnant are not eligible to participate in this study. We ask participants who are capable of becoming pregnant to use appropriate measures (e.g., abstinence, acceptable birth control) to avoid pregnancy. Should a participant become pregnant during the study, they will be told to discontinue all study medications (which represents the key risk during pregnancy) but they will be allowed to remain in the study and receive any remaining coaching interventions and complete all remaining assessments. If a participant becomes pregnant, that is a critical time for them to quit smoking which is something that the cessation counseling in this study can support.

In terms of confidentiality risk, the UW-CTRI Information Technology Administrator, [name], manages the hardware, data, security, and infrastructure below the firewall. Access to the network is limited to only UW-CTRI owned and actively managed devices. All devices automatically lock and are password protected after 15 minutes of inactivity. All portable devices are encrypted for data security and no PHI is stored on local devices. All data stored on the network file server is limited by the principle of least privilege. Healthcare systems will transmit identifying information to UW-CTRI via secure, HIPAA compliant means (either a secure FTP site or a secure interface to the EHR).

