The Data Safety and Monitoring Plan (DSMP) for this Program Project comprises not only the research conducted directly by the University of Wisconsin Center for Tobacco Research and Intervention (UW-CTRI) researchers, but also research conducted by other investigators collaborating with UW-CTRI-funded projects. All investigators must agree to comply with the procedures outlined in this DSMP. This DSMP does not reduce any investigator's obligation to comply with the requirements of the Institutional Review Board (IRB) at his/her home institution or the IRB of any collaborating organizations.

Monitoring the progress of trials and the safety of participants. The Principal Investigators of the Program Project are responsible for routine monitoring of the progress of this research. This includes scheduled biweekly meetings with study staff and review of written documentation of all research projects. Data reviewed at these meetings will include the number and type of participants enrolled, the number and reasons for exclusions from enrollment, the number treated and the stage of intervention, summary of adverse events (AEs), individual review of serious adverse events (SAEs) and study participation, and outcome data. In addition, SAEs or AEs that raise concerns (e.g., allergic reaction, significant change in mood or suicidality) will be immediately reported to the study physician who will determine an appropriate course of action, which may include discontinuation of medication. As data become available, the Director of Research Administration, Project Leader and Principal Investigators will review the data on a regularly scheduled basis (initially biweekly and later monthly) to determine progress. To facilitate participant safety, study participants must meet study inclusion and exclusion criteria. Once enrolled, study protocols will assess the presence of AEs and SAEs at all study contacts. Should either excessive risk to study participants and/or convincing evidence of lack of measurable benefit to study participants be determined, the study will be stopped and all

PROTOCOL
"P01 Cessation Screening Study"
PI: [name].; UW-CTRI Grant:

participants notified in a manner appropriate to the nature of the risk and/or lack of benefit. When taking that step the investigators will consult with the IRB and NCI.

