Additional Analyses. We will examine the main and interactive effects of the 4 factors on the occurrence of adverse events and treatment engagement (count and proportion of counseling sessions completed [1 session for Minimal vs. 4 sessions for Intensive], counseling modality [video vs. phone] chosen for remote protocol participants, count and proportion of medication refills requested [1 for Standard Duration vs. 3 for Extended duration]). Logistic and linear regression will be used for categorical and continuous variables, respectively, with appropriate transformations of continuous variables and/or adoption of generalized regression modeling techniques as necessary. The primary analyses will be unadjusted and then we will statistically control for covariates including: living with a smoker, biological sex, age, clinic, health system, use of other tobacco products at baseline, cigarettes per day at baseline, and education. Analyses of these exploratory outcomes will achieve scientific rigor by controlling for experiment-wise error in families of related tests using the Benjamini-Hochberg approach.

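### The protocol gives conflicting rules on who is asked about adverse events; under the restrictive rule Extended Duration is asked more often than Standard, and the SAP makes no allowance for it

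*Protocol*

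**What the plan says.** Five places in the protocol bear on who is asked about AEs, and they do not agree.

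- Assessments, Calls 7-10: the items include "adverse events (if using study medication", so the question depends on use.
- Table 1 footnote: "Medication use and adverse events will be assessed for participants currently receiving study medication". The footnote adds that this differs between conditions. The table marks AEs at C3 to C9 but not at C10, although the text for Calls 7-10 covers the Week 52 call.
- Assessments, Calls 3-6: the items include "use of alternative nicotine products (e.g., e-cigarettes), withdrawal, self-efficacy, and adverse events", with no on-medication condition. In that sentence the qualifier about study condition attaches to medication use.
- Protection Against Risk: "follow-up protocols will assess for medication side effects and unanticipated health events at all study contacts".
- Data and Safety Monitoring Plan: "study protocols will assess the presence of AEs and SAEs at all study contacts".

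SAP, Additional Analyses: "We will examine the main and interactive effects of the 4 factors on the occurrence of adverse events". The methods named are logistic and linear regression with Benjamini-Hochberg control. No observation window, exposure time or number of assessments is mentioned.

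**The concern.** Staff cannot follow all five statements. If the restrictive ones are followed, a participant is asked about AEs only while on drug, and time on drug is what two of the four factors randomise. A higher AE proportion under Extended Duration would then mix tolerability with the number of times people were asked, and the two could not be separated.

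The rule may also leave a gap among early stoppers. If using means actual use, someone who stopped after Week 4 because of an event is not asked at Week 12 or Week 20.

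Other planned uses draw on the same data. The protocol relates AEs to adherence (Additional Exploratory Analyses). The SAP lists side effects as candidate mediators (Secondary Aims Analyses). The monitoring committee reviews safety by treatment condition.

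**Working it through.** **The plan's own figure.** The documents give no design figure for AEs. Their only power calculation concerns abstinence, with 304 per level and two-sided alpha .05. I reproduced it to check the formula used below:

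power = Φ{[|p2 − p1|√n − 1.96√(2p̄(1 − p̄))] / √[p1(1 − p1) + p2(1 − p2)]}

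This gives 0.871 for 15% vs 25% and 0.814 for 20% vs 30%, against the stated .87 and .81.

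**Medication windows** (Interventions, Preparation Medication and Medication Duration), in weeks from the target quit date:

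- Varenicline, standard preparation: −1 to 11 (Standard Duration) or 23 (Extended).
- C-NRT, standard preparation: 0 to 12 or 24.
- Either drug with 4-week preparation: −4 to 12 or 24.

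**Calls with an AE mark** (Table 1): C3 Week −1, C4 Day 2, C5 Week 2, C6 Week 4, C7 Week 12, C8 Week 20, C9 Week 26.

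**Count of calls inside each window**, applying the footnote to all calls and assuming full use. The first number leaves out calls that fall exactly on a window boundary; the second counts them.

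| Preparation / Duration | Varenicline | C-NRT |
|---|---|---|
| Standard / Standard | 3-4 | 3-4 |
| Standard / Extended | 5-6 | 5 |
| 4 weeks / Standard | 4-5 | 4-5 |
| 4 weeks / Extended | 6 | 6 |

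Week 26 lies after every window. Under this rule C9 yields no AE data from anyone who used medication as scheduled, although Table 1 marks it.

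**Means by factor level:**

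- Duration, boundary calls out: Extended (5+6+5+6)/4 = 5.5; Standard (3+4+3+4)/4 = 3.5; gap 2.0.
- Duration, boundary calls in: Extended (6+6+5+6)/4 = 5.75; Standard (4+5+4+5)/4 = 4.5; gap 1.25.
- Preparation: ON 5.0-5.5, OFF 4.0-4.75; gap 0.75-1.0.
- Medication Type: gap 0-0.25.
- Counseling: gap 0.

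If Calls 3-6 are unconditional, as their own text reads, the Duration gap is still 1.25-2.0 (6.0 vs 4.0-4.75). The Preparation gap falls to 0-0.25, and Medication Type differs by at most 0.25 in either direction.

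**Illustration of size.** Suppose occurrence is analysed as any AE, yes or no, and each assessment has the same chance q of producing a report in every condition. Then P(any AE) = 1 − (1 − q)^k for k assessments, averaged over the cells of a factor level. At q = 10% the values for k = 3, 4, 5, 6 are 0.271, 0.344, 0.410, 0.469.

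- Boundary calls out: Extended (0.410+0.469)/2 = 0.439; Standard (0.271+0.344)/2 = 0.307; difference 13.2 points.
- Boundary calls in: Extended (3×0.469+0.410)/4 = 0.454; Standard (0.344+0.410)/2 = 0.377; difference 7.7 points.

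The last column uses the power formula with (538 − 42)/2 = 248 per level and gives the chance of nominal p<.05, before any Benjamini-Hochberg adjustment.

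| Assumed q | Duration difference, points | Chance of p<.05 |
|---|---|---|
| 5% | 4.9-8.2 | 26-61% |
| 10% | 7.7-13.2 | 41-86% |
| 20% | 9.0-16.6 | 57-97% |

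For Preparation under the footnote rule, the differences are 3.0-4.1, 4.8-6.6 and 5.7-8.4 points. With Calls 3-6 unconditional, the Duration differences are 4.9-7.9, 7.5-12.5 and 8.6-14.7 points.

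**With everyone asked at C3-C9**, all 16 conditions have 7 scheduled assessments, and the difference due to the schedule is 0 for every factor.

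**The case against.** The strongest reply is that the safety sections already promise assessment at every contact and the text for Calls 3-6 has no restriction, so the footnote may be loose drafting. If everyone was in fact asked, the imbalance disappears. That is possible, but the text for Calls 7-10 states the restriction independently, so the conflict has to be resolved in writing.

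A second reply is that longer exposure is part of the Extended policy and can truly cause more AEs. This is correct, and it is why the illustration does not predict the observed difference. It does not justify asking one level more often than the other. The call counts follow from the schedule; the constant per-call chance is only an assumption.

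Third, events that lead to stopping do have a route: the text for Calls 7-10 has them passed to the primary care provider when reported. The footnote's wording could also mean the assigned supply period, in which case early stoppers would still be asked until it ends. Both points limit the concern about stoppers. Neither supplies a scheduled question to people already off drug.

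Fourth, Standard Duration C-NRT and prepared varenicline run to Week 12, so those participants may well count as using medication at that call. The lower end of each range (boundary calls in) allows for this.

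Finally, a comparison limited to the early post-quit calls could not inform Duration, because both levels receive the same medication through Week 4. This stands and shapes the fix.

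**Conclusion.** The point holds as an unreconciled contradiction with a measurable consequence for one factor. Under the restrictive rule, Extended Duration has 1.25 to 2.0 more scheduled AE assessments than Standard, whichever rule governs Calls 3-6. With an equal per-call chance of 5% to 20%, that alone gives a difference in any AE of roughly 5 to 17 points. Preparation is affected only if the footnote governs Calls 3-6. These figures assume full use through the assigned window. The chances of p<.05 also assume 248 per level; the 2:1 allocation period may unbalance Medication Type, and the exclusion of 42 is stated only for the main outcome analyses.

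A reader might infer more than the documents support:

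- That AEs are asked about only on drug. The text for Calls 3-6 and both safety sections say otherwise.
- That all four factors are distorted. Counseling has identical schedules and Medication Type nearly so, although differential stopping could still unbalance either.
- That the effect is the contrast of 3 with 6 calls (27% vs 47% at 10% per call). That compares extreme cells, whereas the SAP tests factor levels.
- That events causing discontinuation go unrecorded. The provider route is partial, but it exists.

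The AE analysis is labelled additional and exploratory. The primary abstinence outcome is not affected.

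**What to change.** Make the text for Calls 3-6, the text for Calls 7-10, Table 1 and its footnote, Protection Against Risk and the Data and Safety Monitoring Plan agree. Every participant should be asked at the same scheduled calls (C3-C9) about AEs since the last contact and the reason for stopping medication, whatever their current use. State whether C10 is included.

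If collection is finished, the SAP should:

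- state which rule was applied in practice;
- report the number of AE assessments by factor level;
- present Duration and Preparation results as on-treatment rates (events per assessment or per person-week on drug) alongside any AE, noting that time on drug is a post-randomisation quantity that AEs themselves can shorten;
- use the first-week, Week 2 and Week 4 window only as a supplementary comparison for Medication Type, Preparation and Counseling, not for Duration, and note that it leaves out pre-quit events under Preparation.

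The cost is a few more questions on calls that already take place, plus one SAP paragraph; if collection is over, only the paragraph and a table of assessment counts.
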